There are numerous versions of mindfulness and mindfulness-based therapies. One approach, Acceptance and Commitment Therapy (ACT), is based on science (as opposed to religion or common sense). ACT helps people to learn about and apply skills to cope with thoughts, emotions and sensations without getting upset, distracted or impeded by them. It also assists people to develop the ability to set clear goals that matter in their life. ACT evaluates successful outcomes in this areas (called 'processes') and how they link to changes in pain, mood and stress. However, more puritan mindfulness courses tend to only focus on the latter.

Research on mindfulness courses for chronic pain, can show that people improve, but not so well what changes in people's experience and skills, or how they apply these. We also know that pain sufferers who attend mindfulness courses for stress, may say it is not so relevant to their pain difficulties.

In this study we want to explore how both mindfulness for stress and mindfulness for pain courses, online, contribute to:

- how specific areas of ACT and other mindfulness learning change

If/how these link with practical skills and any emotional or improvements in the participants' quality of life, use of medication or GP visits. To help us evaluate this, we will ask participants to complete scientifically accepted questionnaires and interview them. We will then use statistical methods and qualitative methods to evaluate change.

This may help us with better supporting chronic pain sufferers with choices around mindfulness as a standalone or as part of attending intensive pain-coping programmes involving different professions.

Scientific abstract of the work proposed

In chronic (persistent) pain, mindfulness can improve coping, depression, quality of life, and reduce pain intensity. Both Acceptance and Commitment Therapy (ACT; Hayes, Strosahl et al. 1999) and mindfulness research, including Mindfulness Based Stress Reduction (MBSR, Kabat-Zinn 1982) and Mindfulness Based Cognitive Therapy (MBCT, Segal, Williams et al. 2002) provide theoretical and/or practical frameworks for *mindful* process measurement.

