However, numerous methodological and contextual limitations exist within the context of pain management centres that are increasingly providing mindfulness based interventions to pain sufferers. This has potential implications for whether implementing mindfulness skills is done with clarity, good governance about whether, where and how it is helpful, or whether it even can be harmful, duplicate other treatments or unnecessarily burden pain sufferers with something that is not needed. In this context, it also has significant implications on any required development of teachers' competencies.

No current research has attempted to unify ACT and other mindfulness process measurement (how people get to change – as opposed to what change they achieve) or to establish the potential contribution and relevance of different specific mindfulness courses in chronic pain patients' treatment pathways and outcomes.

A community-based multidisciplinary-pain-management naïve sample (N=100) of chronic pain patients will be recruited in primary care and placed on a time-set waiting list and then randomly allocated to **one** of two standardised active online mindfulness treatments - stress **or** pain group

conditions. Measurement will include theoretically validated process and outcome measurement. Treatment adherence and fidelity will be independently evaluated from recorded sessions and inter-rater agreement checks performed.

Quantitative analysis will be performed to include descriptive statistics, analysis of variance, session-by-session process change trends, and post-hoc analysis on GP and A&E visits.

Qualitative thematic analysis will complement and bolster the findings of the quantitative phase to include additional process variables unaccounted for by the ACT model, patient experience and descriptive comparison of the two active conditions, including descriptive statistics comparing frequency of reported themes between the two treatments.

i. Aims and objectives:

This study aims to explore and better understand the contribution of standardised group-based mindfulness courses to theoretically valid and coherent mindful-change processes.

OBJECTIVES

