 - a. lack of clarity about providers' competencies and requirements in chronic pain,
 - b. arbitrary removal of essential components of a given intervention,
 - c. often no active or waiting list control condition and
 - d. no consideration at all of utilising a theoretically valid and coherent process-measurement frameworks nor consideration for the teachers' competencies requirements when delivering mindfulness courses to chronic pain patients

(e.g. Dobkin 2008, Day, Jensen et al. 2014, Van Dam, Hobkirk et al. 2014, Day 2017, Harrison, Scott et al. 2017, Hilton, Hempel et al. 2017).

From reviewing the evidence quoted, the research on mindfulness for chronic pain has exclusively utilised standardised mindfulness groups typically aimed at stress populations, excluded less researched pain explicit (contextually relevant to pain) mindfulness group interventions, ignored theoretically valid mindful-process measurement provided by the ACT framework, or not controlled appropriately for significant counfounding factors.

This debate is increasingly important considering that recently published audit data suggests that

mindfulness in one format or the other, or as part of ACT-based multidisciplinary treatment is being provided regularly in pain management centres in the UK . This has been leading, possibly prematurely, to discussion about providing training in mindfulness competencies for pain practitioners such as mindfulness enquiry or leading meditations (e.g. Williams, Watson et al. 2017), which may lead, in turn, to implementing professional skills without sound, targeted and theoretically evidenced rationale.

METHODOLOGICAL ISSUES WITH CURRENT MINDFULNESS RESEARCH AND THE IMPROVEMENTS WITH THIS STUDY

The current research will therefore aim to address and control, some of the currently reported methodological issues in research on group mindfulness based interventions (MBIs), including:

- Utilising a waiting list for the whole group as a control prior to randomisation. This will act as a pseudo treatment-as-usual condition and will track key outcome and process measures across this time.
- Utilising two active interventions, Mfs and MfH-MBPM, with standardised, transparent, comparable in content, time and delivery process that can therefore be easily evaluated for adherence and treatment fidelity.
- Using established and matched teacher's competence in line with UK Network standards (MBTT 2011)for the intervention delivered.

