7. Patients who are actively suicidal, terminally ill or have dementia, cognitive impairment, learning difficulties, or the GP knows of another reason to exclude.

ETHICAL ISSUES

Informed consent

We will obtain approval to contact practices regarding the study with participant's information leaflet and GP information leaflet. We will also obtain informed consent from the treatment providers, including in relation to video/audio feed being recorded. Participants will be offered opportunity to switch off their cameras.

Confidentiality

Data will not be accessed outside the research team. Once collected, checked for inclusion criteria and allocated to a randomly generated participant number, data will be anonymised and prior to the off-site transfer for blind analysis (the statistician will not be aware of which condition stress/pain the participants have been allocated to). Data Transfer Protocols will be utilised in line with the Government of Jersey Governance and Data Protection system, to transfer the data ahead of analysis.

A participant waiting-list randomised, pilot trial of mindfulness based group treatment comparing two active interventions (stress vs pain mindfulness courses) and the waiting-list at recruitment time and 8-weeks post recruitment, coinciding with the start of treatment.

Randomisation will be based on computer-generated random numbers and the sample randomised, will act as a pseudo-waiting-list control for the eight-week waiting period ahead of the intervention.

Recruitment details and Participants

PARTICIPANTS AND DATA COLLECTION

100 people with chronic pain (defined as > three months duration) will be recruited from primary care and social media adverts in Jersey (the social media participants will be

required to register their interest via their GP who will then refer to the lead researcher). Once recruited, participants will be required to complete baseline outcome and process measures, 8-weeks ahead of beginning their 8-week course. Randomisation will take place at this point to either the stress or the pain course. They will repeat this assessment on week 1 of the course and then again at week 4. They will also complete only process measures weekly during the course, in order to explore for links between weekly course content and specific process change.

Posttreatment assessment will be completed within four weeks of treatment completion and at 3-month follow up.

How this study will improve on previous research

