The current study therefore offers an opportunity to impact on the understanding, application of mindfulness and management of chronic pain in the following ways:

- Improved targeting of mindfulness courses as part of multidisciplinary treatment for chronic pain
- A better understanding of the contribution that mindfulness courses may provide in chronic pain patient treatment pathways, as improved understanding of their mindful-process-change relevance, may allow improved targeting and avoid unnecessary duplication, treatment burden or even harm.
- Improving the understanding of the requirement for and development of relevant teaching/training competencies in mindfulness in this area.
- Potentially contributing to establishing whether full mindfulness courses have a place (and what that is) building up to, or as part of multidisciplinary pain management programmes or possibly ahead of these, within the community or as an adjunct to them- for chronic pain sufferers.

Procedure:

100 people with chronic pain (defined as > three months duration) will be recruited from primary care and social media adverts in Jersey (the social media participants will be required to register their interest via their GP). The allocation (stress or pain) will not be concealed from the participants, treatment providers or the researcher. However, analysis of the data will be conducted blind to allocation. Post-treatment assessment will be completed within four weeks of

treatment completion and at 3-month follow up. The sample size has been determined to recruit 8-12 participants for each of four stress and pain courses to be administered with a recruitment of 50 and a minimum target of 30 per active intervention.

Qualitative study:

DESIGN AND SETTING

A qualitative study involving semi-structured interviews will be held, with a topic guide informed by the ACT psychological flexibility model (Hayes, Strosahl et al. 1999) and Day's framework for mindfulness-relevant processes (Day, Jensen et al. 2014) in chronic pain, and based on mindfulness research improvement based on adaptations of Mindfulness Based Cognitive Therapy (MBCT) for chronic pain (Day 2017).

Exclusion criteria (in addition to quantitative study criteria):

Non-completers (participants who completed less than 6/8 course sessions)

Declined to take part in interviews

SAMPLING

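### The plan randomises 8 weeks before the course with no rule on when participants are told, but elsewhere puts the wait first; fix the order or withhold the result until the pre-course assessment is in

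*Combined protocol and SAP*

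**What the plan says.** Part 3, section 2.iii puts allocation first and the wait second. Under Participants and data collection, "participants will be required to complete baseline outcome and process measures, 8-weeks ahead of beginning their 8-week course", and the next sentence reads "Randomisation will take place at this point to either the stress or the pain course". The randomisation paragraph shortly before it says that the randomised sample "will act as a pseudo-waiting-list control for the eight-week waiting period ahead of the intervention". The Procedure paragraph adds: "The allocation (stress or pain) will not be concealed from the participants, treatment providers or the researcher". Only the data analysis is blind.

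Two other places give the reverse order. The scientific abstract has participants "placed on a time-set waiting list and then randomly allocated to" one of the two courses. The list of methodological improvements in section 2.ii offers "Utilising a waiting list for the whole group as a control prior to randomisation".

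Four further points matter here:

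- On the pre-treatment assessment, the plan says: "They will repeat this assessment on week 1 of the course and then again at week 4". It does not say whether this comes before or after session 1.
- The lay abstract says that pain sufferers who attend stress courses "may say it is not so relevant to their pain difficulties".
- Post-hoc analysis (section 2.iv) compares GP and A&E visits in the waiting period with those between the end of treatment and follow-up.
- Main analysis names ANOVA and ANCOVA but gives no analysis set and no rule for people lost before session 1.

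Nothing in the available text says when a participant is told the allocation.

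**The concern.** Everyone recruited has chronic pain, and one of the two courses is explicitly about pain. Someone who learns at baseline that they have the stress course has 8 weeks in which to feel that they drew the less relevant option, to seek help elsewhere, or to withdraw. Someone given the pain course has less reason to do so. This is separate from concealing the sequence at enrolment: a perfectly concealed list does not help if the result is disclosed 8 weeks before anything is delivered.

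Three things depend on the wait being neutral between arms:

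- The wait is the trial's only untreated comparison, the pseudo-treatment-as-usual period.
- The week-1 score is the last value before teaching. If it carries hope or disappointment about the allocation, it is not a clean pre-treatment value.
- The waiting-period count of GP and A&E visits is the comparator for the post-hoc analysis, and help-seeking prompted by allocation would enter it directly.

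If withdrawal during the wait also differs by arm, the people who start the two courses are no longer the groups that were randomised.

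**Working it through.** **Step 1. The two sequences side by side.**

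| Source | Order | Can an arm be known during the wait? |
|---|---|---|
| Participants and data collection; randomisation paragraph | baseline, randomise, 8-week wait, course | yes, unless withheld; no text withholds it |
| Scientific abstract; improvements list in the Rationale | wait, randomise, course | no, because no allocation exists yet |

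Both cannot hold. The problem arises only under the first order, which is the one in the operational text.

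**Step 2. A simple illustration.** The documents give no withdrawal rate for the wait and no outcome SD, so the inputs other than 50 per arm (Procedure) are assumptions. Let a fraction p of an arm withdraw, with withdrawers scoring d SD worse than stayers. The arm mean is then the stayers' mean minus p × d, so the stayers look better than their full arm by p × d.

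- Assumed p = 0.25 (stress) and 0.10 (pain), d = 0.5.
- Starters: 50 × 0.75 = 37.5 and 50 × 0.90 = 45.
- Shift: 0.25 × 0.5 = 0.125 SD and 0.10 × 0.5 = 0.05 SD.
- Difference between arms: 0.125 − 0.05 = 0.075 SD, here flattering the stress course.
- At 5% v 5% with the same d, the difference is 0.

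The direction depends entirely on withdrawers being worse. If they were better, the sign would reverse.

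**Step 3. A range.** Let withdrawal propensity and outcome be jointly normal with correlation ρ (assumed 0.2 to 0.5), and let a fraction w withdraw. The stayers' mean shifts by ρ × φ(c)/(1 − w), where c is the (1 − w) normal quantile. The factor φ(c)/(1 − w) is 0.195 at w = 0.10, 0.350 at 0.20, 0.497 at 0.30 and 0.644 at 0.40.

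| Assumed withdrawal | Difference in factors | Bias at ρ = 0.2 | Bias at ρ = 0.5 |
|---|---|---|---|
| 30% v 10% | 0.302 | 0.06 SD | 0.15 SD |
| 40% v 20% | 0.294 | 0.06 SD | 0.15 SD |
| 40% v 10% | 0.449 | 0.09 SD | 0.22 SD |
| 20% v 20%, same selection | 0 | 0 | 0 |
| 20% v 20%, opposite selection | 0.350 + 0.350 = 0.700 | 0.14 SD | 0.35 SD |

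The last row shows that equal withdrawal rates alone do not guarantee balance.

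**Step 4. Scale.** The plan gives no power calculation to reproduce. Its targets of 50 recruited and at least 30 per arm tolerate 1 − 30/50 = 40% loss over the whole study. At an assumed two-sided 5% level and 80% power, the detectable effect is (1.960 + 0.842) × √(2/n). That is 0.56 SD at n = 50 and 0.72 SD at n = 30.

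**Step 5. Would a later check reveal it?** Take 50 per arm and a test of two proportions with pooled variance under the null. For 30% v 10%, (0.20 − 1.96 × 0.0800)/0.0775 = 0.56, which is 71% power. For 40% v 20%, (0.20 − 1.96 × 0.0917)/0.0894 = 0.23, which is 59% power. A non-significant comparison of withdrawal would therefore not rule out a 20-point difference.

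**The case against.** The strongest reply is that the problem may not exist. Two passages put the wait before randomisation; if they describe the real intention, nobody has an arm during the wait. That stands as a reason to reconcile the text, but not to leave it, because the operational section says the opposite.

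Second, early disclosure is an inference. A reader might conclude that the sponsor has decided to tell participants at baseline. The documents do not support that: the statement on non-concealment describes an open-label trial and carries no date, and the invitation letter and information sheet, listed as enclosures, are not in the text available here. What stands is that no rule in this text prevents early disclosure.

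Third, a reader might take the lay abstract as evidence that stress-arm participants will drop out. It reports what people who attend such courses may say; the documents hold no data on withdrawal during a wait. It makes the mechanism plausible and no more.

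Fourth, a score untouched by allocation already exists at baseline, and ANCOVA is planned. Adjusting for that score would reduce bias from selection related to baseline severity. The covariates are not named, however, and adjustment restores neither the wait nor the visit counts.

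Fifth, mindfulness participants cannot be blinded. That is true once teaching starts, but nothing arm-specific need be delivered during the wait.

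Finally, 0.075 SD is small beside 0.56 to 0.72 SD, in a pilot without formal predictions of effect. That is fair, and it limits the weight of the point.

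**Conclusion.** The concern holds in a limited form. The documents contradict themselves on whether randomisation comes before or after the wait. Under the operational order they leave participants able to know their course for 8 weeks. The pseudo-treatment-as-usual period, the week-1 score and the waiting-period visit count are then open to differences by arm.

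The size cannot be established from the documents. The illustrations run from 0 to 0.35 SD, and every withdrawal rate, score gap and correlation behind them is assumed. The upper end needs selection in opposite directions in the two arms.

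A reader might also infer that withholding the result makes the people who start the courses comparable. It does not. A participant told just before session 1 can still withdraw at that moment, so only the wait and the pre-treatment score are protected. The change is worth making because it is cheap and the wait is the only untreated period the trial has, not because a large bias has been shown.

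**What to change.** Reconcile the scientific abstract, the improvements list in section 2.ii and the two 2.iii paragraphs on one order. Either of these resolves the point:

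1. Randomise after the 8-week wait, once the pre-course assessment has been submitted.
2. Randomise at baseline, but withhold the result until that assessment is submitted, both from participants and from staff in contact with them. The lead researcher is contactable throughout and is not blind under Procedure, so someone else would have to hold the list.

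Under either option:

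- State that the week-1 assessment is completed before session 1 and before the course book and joining link are sent.
- Report withdrawals by arm and by time, before and after disclosure. Under option 1, those who leave during the wait have no arm and are reported as one group.
- Analyse all randomised participants as allocated, and say how missing scores are handled.

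The cost is wording, later mailing and shorter notice of the course. Recruitment stays at 100 and no visit is added; under option 1 the number randomised is whoever remains after the wait. The two courses need not run at identical times, which could require teachers to be available simultaneously: participants can hold a slot without being told which course it is.

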- Utilising the same 'dosage' and type of interventions (groups with similar structure, delivery times and requirements for practice) utilising MfH-MBPM and MfS (Burch and Penman 2013, Hennessy 2017)
- Using appropriate psychometric and qualitative analysis and targetting of explicit process-change.
- Reporting adverse side effects
- Measures in line with IMMPACT recommendations for research on chronic pain (Dworking *et al.*, 2005).

iii. **Study design, to include recruitment and sampling strategy, inclusion/exclusion criteria, sample size and justification:**

In order to address the research questions, the current study will be divided in and presented as separate quantitative and qualitative components:

Quantitative study:

Design and Method

DESIGN

A waiting-list controlled, randomised, pilot trial of mindfulness based group treatment comparing two active standardised interventions (mindfulness for stress vs. mindfulness for pain/health)

SETTING AND STUDY POPULATION

An opportunity sample via general practice, waiting-room advert and GP supported recruitment in Jersey, serving a population of 106,000, will be invited to take part in the study.

RECRUITMENT

All general practices in Jersey will be invited to take part in this study. They will be recruited through the Jersey Primary Care Body and Social Media Advertising.

CASE IDENTIFICATION

Over a six months period.

Once potential participants have consented, searches will be run on GP electronic health records to identify suitability. Demographic data including gender, age, ethnicity and employment status, pain diagnoses, current medication and dosage, co-morbidities and mental health diagnoses will be extracted via GP referral to the study, including that the patients meet inclusion criteria and do not meet any of the exclusions.

INCLUSION AND EXCLUSION CRITERIA (PATIENTS)

Inclusion criteria:

1. Pain > 3 months
2. Ability to communicate and literacy in English
3. Age 18 years or older
4. No current outstanding medical tests or procedures for conditions expected by the GP to interfere with participation in treatment.
5. Has not previously received non-medical treatment at a specialist pain centre, or

attended a multidisciplinary pain management programme.

6. Ability to utilise online video conferencing technology (i.e. ownership of a compatible device & necessary technical competence)

Exclusion criteria:

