An opportunity sample from all patients invited to take part to the quantitative research aspect, invited as part of the initial quantitative study informed consent process.

We will invite all participants from the sample, aiming from 10-15 participants from each the stress and pain version of the courses, hence a total sample of 30 participants maximum and a target of 10 completed interviews for each intervention.

iv. Proposed method(s) of data analysis

Quantitative:

PRELIMINARY ANALYSIS

After randomisation, we will carry out preliminary baseline analysis using independent group t-tests to establish no significant demographic (age, education, duration of pain, number of comorbid medical conditions, visits for pain the past three months) or psychometric differences between the groups. This will act as a pseudo-waiting list treatment-as-usual (TAU) control group.

MAIN ANALYSIS

Treatment process change and outcomes

Means, Standard Deviations (SDs), between-group analysis of variance and co-variance (ANOVA, Between-Group ANCOVA) results and effect sizes (Between-Group effect sizes: d) for pretreatment, session-by session process change tracking including a practical selection of accepted and validated process-change measurement for all six areas of psychological flexibility and outcome measurement related to:

- pain intensity and interference
- impact on functioning
- emotional functioning (depression, pain catastrophizing)
- Global impression of functioning

for baseline, half-way, end-of-treatment and follow up

Analysis will be performed utilising SPSS.

These will include a practical selection of primary outcome measures, treatment process measures, as well as measures of emotional functioning, patient rating of change and change in medication use.

Post-hoc analysis

Will include number of GP and A&E visits comparing the waiting period and from the end of treatment to follow up.

STATISTICAL POWER

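### GP and A&E visit counts over an 8-week wait are compared with counts over about 3 months, with no rate or offset, so an unchanged visit rate would look like a rise of about 63% (3 months taken as 13 weeks)

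*Combined protocol and SAP*

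**What the plan says.** The comparison is set out in one sentence, under Post-hoc analysis in Part 3, section 2.iv: "Will include number of GP and A&E visits comparing the waiting period and from the end of treatment to follow up". The only other mention is in the scientific abstract, whose list of analyses ends with "session-by-session process change trends, and post-hoc analysis on GP and A&E visits". That names the analysis and adds no method.

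The length of the first window is clear. The abstract has participants "recruited in primary care and placed on a time-set waiting list". Section 2.iii describes the randomised sample as a "pseudo-waiting-list control for the eight-week waiting period ahead of the intervention", and under Participants and data collection they "complete baseline outcome and process measures, 8-weeks ahead of beginning their 8-week course".

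The second window is less clear. Section 2.iii says: "Posttreatment assessment will be completed within four weeks of treatment completion and at 3-month follow up". The Procedure paragraph repeats this timing. Neither place says what the 3 months are counted from.

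One other visit variable appears: the Preliminary analysis paragraph lists "visits for pain the past three months" among the baseline characteristics to be compared between groups.

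**The concern.** The quantity named is a number of visits, and the two periods over which it is counted differ in length on nearly every reading of the plan. A longer window collects more visits even if nobody's behaviour changes. With no rate, offset or matched window, the before/after comparison mixes any change in visit rate with the difference in observation time.

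A real fall in service use after the course could be hidden, or reported as a rise. This does not depend on a significance test, because two raw totals shown side by side mislead in the same way. The lay abstract names GP visits (though not A&E visits) as something the study will look at, so a reader would expect this result to be interpretable.

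The baseline visit item does not solve the problem. Its look-back is closer in length to the second window, but it covers pain visits only and is not linked to this analysis.

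**Working it through.** The plan gives no visit rate, test or expected result for this comparison, so there is no figure to reproduce. The check asks what the stated comparison would show if the visit rate did not change.

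**Inputs**

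- Waiting period: 8 weeks (section 2.iii).
- Follow-up: 3 months (section 2.iii). The plan does not give this in weeks, so M = 13 is assumed and M = 12 is shown beside it.
- Delay *d* from the last session to the post-treatment assessment: 0 to 4 weeks (section 2.iii).

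**Length of the second window, L**

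Two starting points are unstated: where the end of treatment falls, and where the 3 months begin. Each could be the last session or the post-treatment assessment.

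- Both the same: L = M.
- Window opens at the assessment, 3 months run from the last session: L = M − d.
- Window opens at the last session, 3 months run from the assessment: L = M + d.

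**Apparent change with a constant visit rate**

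The expected count is rate × weeks, so the ratio of expected counts is L/8.

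| Reading | M = 13 | M = 12 |
|---|---|---|
| Same starting point | 13/8 = 1.625 | 12/8 = 1.50 |
| M − d, d = 2 | 11/8 = 1.375 | 10/8 = 1.25 |
| M − d, d = 4 | 9/8 = 1.125 | 8/8 = 1.00 |
| M + d, d = 2 | 15/8 = 1.875 | 14/8 = 1.75 |
| M + d, d = 4 | 17/8 = 2.125 | 16/8 = 2.00 |

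The d = 4 rows apply only to a participant assessed on the last permitted day. The windows are equal in one cell only: 3 months read as 12 weeks, the shortest choice of starting points and the longest delay.

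**True fall in rate that would look like no change: 1 − 8/L**

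- M = 13: 1 − 8/13 = 38% (from 1 − 8/9 = 11% to 1 − 8/17 = 53%).
- M = 12: 1 − 8/12 = 33% (from 0% to 1 − 8/16 = 50%).

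**How a true 25% fall would appear: 0.75 × L/8**

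- M = 13: 0.75 × 13/8 = 1.22, a 22% rise (from 0.75 × 9/8 = 0.84, a 16% fall, to 0.75 × 17/8 = 1.59, a 59% rise).
- M = 12: 0.75 × 12/8 = 1.125, a 13% rise (from 0.75, the true fall, to 1.50, a 50% rise).

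**After standardising**

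Dividing each count by its own weeks gives a ratio of 1.00 when the rate is constant, whatever L is.

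These are ratios of expected counts. They do not depend on the visit rate, its dispersion, the sample size or the test. No false-positive rate is claimed, since that would need a test, a visit rate and within-person variation, none of which the plan gives.

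**The case against.** The strongest reply is that the sentence is a brief description in an ethics application. It names a quantity and two periods but no summary statistic or model, and nothing in it rules out standardising. A careful analyst might well do so. But nothing requires it, and the quantity actually named is a number. Rates also need windows with defined ends, which the plan does not supply. If visits are collected by recall questions that name no window, the gap could not be repaired at analysis.

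Second, the net bias may not be upward. Recruitment runs through general practice, including waiting-room adverts, so people may enter at a time of above-average GP use and drift down without any treatment effect. That is plausible and its size is unknown. It is a separate bias and does not change the length ratio, but it does limit the claim made here to the effect of window length alone.

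Third, 63% is one point in a wide range that depends on assumptions. This is accepted: the range is 1.00 to 2.13, and only its lowest value shows no distortion.

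Fourth, the stakes are modest. The study is "A waiting-list controlled, randomised, pilot trial of mindfulness based group treatment", the analysis is labelled post-hoc, and visits are not in the list of outcome measures. The stress-versus-pain contrast over the same window is not biased if follow-up timing is alike in both arms. The window-length error would also understate a benefit and not create one. All of this stands, and it limits how much the point matters. It does not make the comparison sound.

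**Conclusion.** The concern holds. As written, the comparison would show a rise in visits with no change in visit rate: about 63% if 3 months is 13 weeks and both starting points agree, 50% if it is 12 weeks, and between 0% and 113% across every reading considered. The 8-week wait is stated in the plan. The conversion of months to weeks and the choice of starting points are assumptions. The direction of the window-length effect is the same on every reading except the single case of equal windows.

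The plan should be changed, but this does not threaten the trial's main question. The effect is confined to the before/after comparison of visits.

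**What to change.** - State whether the end of treatment, and the start of the 3 months, is the last session or the post-treatment assessment.
- Define the start and end of both windows, and record each participant's weeks observed in each.
- Replace the number of visits with GP and A&E visits per week observed, compared within participant as a mean difference.

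A repeated-measures count model with log(weeks observed) as offset is an acceptable alternative. It estimates a rate ratio and not a mean difference, so the plan should name one of the two. Equal 8-week windows would also work, but only if visits are recorded with dates.

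The cost is small: one or two sentences of analysis text and one recorded field per window. The plan does not say how visits are captured; the search of GP records described under Case identification is for suitability and referral data. If visits come from recall questions, those questions need to name the window.
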